The COVID-19 pandemic caused by the SARS-CoV-2 virus was declared by the WHO on 11 March 2020 (WHO 2020). As of 11 November 2021, more than 250 million cases have been reported worldwide, leading to more than 5.0 million deaths (WHO 2021). To date, there are several vaccines available, licensed, under emergency use authorizations or conditional approvals using different technologies. All available vaccines utilize antigens from the ancestral Wuhan strain (D614; wild-type, hereafter referred to as "WT").

This is a Phase 1 first-time-in-human study designed to evaluate the safety, reactogenicity, and immunogenicity of the GSK-CureVac second-generation CV2CoV vaccine to prevent COVID-19 disease caused by existing and new emerging strains of the SARS-CoV-2 virus. This study will evaluate the CV2CoV vaccine in a booster vaccination setting.

CureVac developed a first-generation mRNA vaccine (CVnCoV) using WT, for which vaccine safety and efficacy are being evaluated (NCT04652102). To continue addressing current vaccine needs for further protection against SARS-CoV-2, GSK and CureVac are collaborating to develop CV2CoV mRNA second-generation vaccine based on CureVac's mRNA vaccine platform. The CV2CoV vaccine is based on a new mRNA backbone that features targeted optimizations designed to improve intracellular mRNA stability and translation for increased and extended protein expression. These optimizations potentially allow for strong immune responses at low doses, which are intended to support the development of future multivalent vaccines to target rapidly spreading COVID-19 variants (CureVac 2021).

This statistical analysis plan (SAP) was developed to provide the details of the planned statistical methodology for the final analysis and the 2 interim analyses (Section 12).

This SAP is based upon the following study documents:

- Study Protocol 217741 (CV2 SARS-COV2-002 BST) Protocol Amendment 2 (27 May 2022)
- Participant Case Report Form Version 5.0 (20 Oct 2022)

This SAP is to be finalized prior to first participant first visit. Major changes in the analysis that are made after database lock will be documented in the CSR along with the rationale and other details regarding the changes.

2. Objectives

[figure not shown]
2.1. Primary Objective and Endpoints

Objectives	Endpoints
Primary – Safety	
To evaluate the safety and reactogenicity of CV2CoV at each dose level in SARS-CoV-2 seropositive healthy adult participants after booster vaccination	• Percentage of participants with MAAEs, SAEs, and AESIs from study vaccination through the end of the study (approximately 180 days after the study vaccine administration, Day 1 through 180), each summarized separately
	• Percentage of participants with each solicited local and systemic AE within the 7-day postvaccination period (Days 1 to 7)
	• Percentage of participants with unsolicited AEs up to 28 days after study vaccination, including clinically relevant abnormal laboratory findings (Day 1 through Day 28)

2.2. Secondary Objectives and Endpoints

Objectives	Endpoints
Secondary – Immunogenicity	
To explore the dose response and effect of CV2CoV at each dose level on neutralizing Ab titers against pseudovirus bearing spike protein from SARS-CoV-2 WT in SARS-CoV-2 seropositive healthy adult participants after booster vaccination	 GMTs of neutralizing Ab titers against pseudovirus bearing spike protein from either SARS-CoV-2 WT at each collection time point (Days 1, 8, 15, 29, 85, and 180) Percentage of participants with seroresponse (≥4-fold rise from baseline) at Day 29 after the booster dose. GMI from baseline of neutralizing Ab titers against pseudovirus bearing spike protein from SARS-CoV-2
	WT at each collection time point (Days 8, 15, 29, 85, and 180)
To describe serum binding Ab (IgG) levels specific for vaccine antigens in SARS-CoV-2 seropositive healthy adult participants after	• GMTs of binding IgG against SARS-CoV-2 S protein and RBD at each collection time point (Days 8, 15, 29, 85, and 180)
booster vaccination	• GMI from baseline of binding IgG against SARS-CoV- 2 S protein and RBD at each collection time point (Days 8, 15, 29, 85, and 180)

2.3. Tertiary Objectives and Endpoints

3. Investigational Plan

3.1. Overall Study Design and Plan

This Phase 1 study will evaluate the safety, reactogenicity, and immunogenicity of the CV2CoV vaccine in SARS-CoV-2 seropositive healthy adult participants. The study will be conducted in 5 sequential cohorts with dose escalation from 2 μ g to 20 μ g. Each cohort will include the dose and age groups as indicated in Table 3-1. A study design schematic is provided in Figure 3-1.

A total of up to approximately 180 healthy adult participants will be enrolled, 30 per dose group. The 30 participants will be distributed between the younger (\geq 18 to <65 years old) and older (\geq 65 years old) age groups, with a minimum of 10 and a maximum of 20 participants in each age group. There will be 3 sentinel participants in each age group within each dose group. (Table 3-1).

The screening period will be up to 14 days, study vaccine administration will occur on Day 1, and participants will have approximately 180 days (6 months) of follow-up after study vaccine administration. The study will be open label.

Participants in all cohorts will be screened for eligibility up to 14 days before enrollment. Participants will receive study vaccine according to their cohort (Table 3.1-1), dose group, and age group; and study visits will proceed according to the schedule of events (SOE) provided in Appendix 15.1. Participants will be sequentially enrolled to the dose level assigned to their cohort.

Enrollment in each dose cohort and the progression from vaccination in younger to older adult participants will be staggered based on SRT data review will progress as described in protocol Section 7.8. Holding rules for dosing are described in protocol Section 5.9.

Three sentinel participants in the younger age group (Cohort 1) will be enrolled before opening enrollment to the older age group (Cohort 1).

Escalation to the next higher dose cohorts will be based on the SRT review of safety data from the same age group.

[figure not shown]
Enrollment into Cohorts 2 and 3 (8 and 12 μ g, respectively) will begin after the SRT has reviewed Days 1 to 8 safety data (including Day 8 laboratory data) from 3 sentinel participants from the previous dose cohort. Enrollment into Cohorts 4, and 5 (16 μ g, and 20 μ g, respectively), will begin after the SRT has reviewed Day 1 to 8 safety data (including Day 8 laboratory data) from all participants in the previous dose cohorts.

A first interim analysis of safety and immunogenicity data up to 14 days after study vaccine administration in participants enrolled in Cohorts 1, 2, and 3 will be performed. A second interim analysis of safety and immunogenicity data will be performed 14 days after participants in Cohorts 4 and 5 have received study vaccine.

Cohort	Dose Group	Dose Level	Younger Adults ≥18 to <65 Years of Age	Older Adults ≥65 Years of Age	Total Dose Group Sample Size
1	1a	2 µg	$10 \le n \le 20$	$10 \le n \le 20$	30
	1b	4 μg	$10 \le n \le 20$	$10 \le n \le 20$	30
2	2	8 μg	$10 \le n \le 20$	$10 \le n \le 20$	30
3	3	12 µg	$10 \le n \le 20$	$10 \le n \le 20$	30
4	4	16 µg	$10 \le n \le 20$	$10 \le n \le 20$	30
5	5	20 µg	$10 \le n \le 20$	$10 \le n \le 20$	30

 Table 3.1-1: Study Cohorts, Groups, and Study Vaccine Administration

Figure 3.1-1Study Design Figure

[figure not shown]

3.2. Study Endpoints

Please refer to Section 2 of this SAP.

3.3. Treatments

Investigational product (IP) refers to the CV2CoV vaccine that will be administered during the study.

chloride.

The following IP will be used in the study:

	Investigational Product	
Description	CV2CoV ^a	
CCI	CCI	
	WT CCI	
CCI	CCI	
a. Product reference: CV07050201.		
b. CCI		

3.4. Overdose Management

An overdose is any dose of study vaccine given to a participant that exceeds the planned dose for an individual within a given dose group.

There is no specific treatment recommended for an overdose. Overdose itself is not to be reported as an AE, however, any AEs associated with the overdose will be analyzed as relevant AEs/SAEs. Overdose participants will be included in the Safety Set and excluded from Per Protocol (PP) Set.

4. General Statistical Considerations

Participants will be identified in the listings by the participant identification number concatenated with the site number. Data will be displayed in all listings sorted by age group, dose group and participant number.

Continuous data will be described using descriptive statistics (n, mean, standard deviation, median, minimum, and maximum). **Categorical data** will be described using the participant count and percentage for each category.

For the **summary statistics** of all numerical variables unless otherwise specified, mean, confidence interval, median, standard deviation, minimum and maximum will be displayed.

A row denoted "Missing" will be included in count tabulations where specified on the shells to account for dropouts and missing values.

There is no formal hypothesis testing in this study where statistical methods are applied; the emphasis will be on estimation with 2-sided 95% CIs.

The denominator for all percentages will be the number of participants with non-missing values of corresponding parameter in that treatment within the analysis population of interest, unless otherwise specified.

A table, figure, or listing is to be generated for any required item even where no data is available or reported. In such cases, the outputs will state: "**No Data Reported**". This will confirm to the health authorities that all data for the tables, figures, listings, and narratives are accounted for.

If a participant has no data they will be excluded from the specific output.

Baseline will be defined as the last non-missing evaluation prior to study vaccine administration, unless otherwise specified.

Study day will be calculated as follows:

- a) study day prior to the injection will be calculated as: date of assessment date of the injection
- b) study day on or after the date of the injection will be calculated as: date of assessment date of the injection + 1

For Safety assessment of AEs, the intervals will be calculated as follow

- solicited AEs: the day of vaccination and 6 subsequent days (Day 1 through 7)
- unsolicited AEs: the day of vaccination and 28 subsequent days (Day 1 through 28)
- Medically attended adverse events (MAAEs), adverse events of special interest (AESI) and serious adverse events (SAEs): the day of vaccination and 180 subsequent days (Day 1 through 180)

For calculations regarding antibody levels/titers, antibody values reported as below the lower limit of quantification (LLOQ) will be replaced by $0.5 \times \text{LLOQ}$. Values that are greater than the

upper limit of quantification (ULOQ) will be converted to the ULOQ. Missing results will not be imputed.

The LLOQ and ULOQ for NAb are the following: LLOQ = To be defined by lab when assay calibrated. ULOQ = To be defined by lab when assay calibrated. calibrating conversion factor to WHO standard is 1/1.872. NAb Result (IU/mL) = Result (NT50 titer) x 1/1.872. Details on LLOQs and ULOQs for IgG and conversion factors are described in Appendix 15.2. All safety data will be summarized by dose group. All statistical analyses will be performed using SAS[®] software Version 9.4 or later.

4.1. Sample Size

The sample size is based on clinical considerations to inform dose regimen decisions for continued clinical development. Approximately 180 participants will be enrolled in this Phase 1 study, with 6 dose-level cohorts each comprising 2 age groups. With 30 participants in each cohort, there is a 78.5% probability to observe at least 1 AE if the incidence rate is 5% and a 95.8% probability to observe at least 1 AE if the incidence rate is 10%. With 30 participants in each cohort, a 10% unevaluable rate for immunogenicity results, and a standard deviation of 0.45 for log10-transformed increase from Day 1, the ratio of the upper limit of a 2-sided 95% CI and the point estimate of Geometric Mean Increase (GMI) is 1.5.

4.2. Randomization, Stratification, and Blinding

Participants in Cohort 1 will be randomized to receive either the 2 μ g or 4 μ g dose levels; participants in the other cohorts will be sequentially enrolled to the dose level assigned to their cohort.

Three sentinel participants in the younger age group (Cohort 1) will be enrolled before opening enrollment in the older age group (Cohort 1).

The study will be open label.

4.3. Analysis Set

The following analysis sets have been defined: Enrolled Set, Per Protocol (PP) Set, and Safety Set.

4.3.1. Enrolled Set

The Enrolled Set will include all participants who have a signed informed consent form (ICF) and were assigned to a group, vaccinated, or had an immunogenicity blood draw. The Enrolled Set will be used for participant disposition, protocol deviation and enrollment by public disclosure required age category summaries.

4.3.2. Per Protocol Set

The Per Protocol (PP) Set will include all eligible participants who received a dose of study intervention IP as per protocol and who have values for predose and Day 29 neutralizing Ab titers against pseudovirus bearing S protein from ^{CCI} Results from a blood sample deviating from the dosing or blood sampling schedule (Appendix 15.1) and results from a blood sample after intercurrent conditions that may interfere with immunogenicity (eg, virologically confirmed SARS-CoV-2 infections or immunodeficient conditions) or from participants who received COVID-19 vaccination within 29 days postvaccination will be excluded from the PP Set. The analysis will be done according to the dose that participants received at Day 1.

The PP Set will be used for the analysis of immunogenicity, demography and the analysis of PBMC subset.

Significant protocol deviations will be reviewed and may lead to exclusion from the PP Set.

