7.3 Analysis Sets

The following analysis sets will be used in the statistical analyses.

- Enrolled Set: All participants who have a signed ICF and were assigned to a group, vaccinated, or had an immunogenicity blood draw.
- Per Protocol Set: The PP set includes all eligible participants who received a dose of study intervention IP per protocol and who have values for predose and Day 29 neutralizing Ab titers against pseudovirus bearing S protein from Results from a blood sample deviating from the dosing or blood sampling schedule (Table 13-1) and results from a blood sample after intercurrent conditions that may

interfere with immunogenicity (eg, virologically confirmed SARS-CoV-2 infections or immunosuppressive or immunodeficient conditions) or from participants who received COVID-19 vaccination within 29 days postvaccination will be excluded from the PP set. The analysis will be done according to the dose that participants received at Day 1. The PP set will be used for the immunogenicity analyses.

• Safety Set: All participants who received any IP. All analyses using the Safety Set will group participants according to the study vaccine actually received. The Safety Set will be used for safety analyses.

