7.7 Interim Analyses

A first interim analysis of safety and immunogenicity data covering at least neutralizing Ab titers against pseudovirus bearing S protein from up to 14 days after study vaccine administration in all participants enrolled in Cohorts 1, 2, and 3 will be performed. A second interim analysis of safety and immunogenicity data will be performed 14 days after participants in Cohorts 4 and 5 have received study vaccine. Details of these interim analyses will be described in the SAP.

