9.5. Electrocardiogram

Not applicable.

10. Pharmacokinetics

Not applicable.

11. Pharmacodynamics

Not applicable.

12. Interim Analysis

A first interim analysis of safety and immunogenicity data covering at least neutralizing Ab titers against pseudovirus bearing S protein from ^{CCL} up to 14 days after study vaccine administration in participants enrolled in Cohorts 1, 2, and 3 will be performed including at least day 1 and day 15 data. A second interim analysis of safety and immunogenicity data covering at least neutralizing Ab titers against pseudovirus bearing S protein from ^{CCL} was planned, however this was cancelled as the study was closed early.

13. Changes in the Planned Analysis

Not applicable.

14. References

Department of Health and Human Services (DHHS), Food and Drug Administration, Center for Biologics Evaluation and Research (US). Guidance for industry. Toxicity grading scale for healthy adult and adolescent volunteers enrolled in preventative vaccine clinical trials. September 2007 [cited 2021 Jul 09]. Available from: https://www.fda.gov/media/73679/download

World Health Organization (WHO). WHO coronavirus (COVID-19) dashboard [Internet]. 2021 [cited 2021 Jul 07]. Available from: https://covid19.who.int/

15. Appendices

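### The Per Protocol Set requires a Day 29 titer even for Day 8, Day 15 and PBMC analyses, so valid early results are dropped for want of a later sample

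*SAP*

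**What the plan says.** **Membership.** SAP 4.3.2 limits the PP Set to eligible participants dosed per protocol "who have values for predose and Day 29 neutralizing Ab titers against pseudovirus bearing S protein". Protocol 7.3 sets the same condition. The text after the quoted words is partly redacted, but that gap concerns the strain and not the Day 29 requirement.

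**Use.** The SAP states: "The PP Set will be used for the analysis of immunogenicity, demography and the analysis of PBMC subset". The protocol states: "The PP set will be used for the immunogenicity analyses".

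**Other sets.** SAP 4.3 closes the list: "The following analysis sets have been defined: Enrolled Set, Per Protocol (PP) Set, and Safety Set". The Enrolled Set serves disposition, deviations and age-category summaries (SAP 4.3.1); for antibody data it appears only in supporting listings (SAP 8.2.1). The Safety Set serves safety and demography (SAP 4.3.3).

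**First interim.** Protocol 7.7 describes safety and immunogenicity data "up to 14 days after study vaccine administration in all participants enrolled in Cohorts 1, 2, and 3 will be performed" and leaves the details to the SAP. SAP 3.1 repeats the window: "immunogenicity data up to 14 days after study vaccine administration in participants enrolled in Cohorts 1, 2, and 3". SAP Section 12 adds that the analysis "will be performed including at least day 1 and day 15 data". It names no analysis set for this interim and no exception to the Day 29 condition. The second interim "was planned, however this was cancelled as the study was closed early".

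**Early-visit outputs.** GMTs and GMIs at Days 8 and 15 are secondary endpoints (SAP 2.2). A Day 15 seroresponse summary is planned as supportive (SAP 8.2.2). Blood for PBMC is drawn only on Days 1 and 15 (schedule of events in both documents).

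**The concern.** A membership rule for an analysis should depend on what that analysis needs. Here one participant-level condition, a sample due on Day 29, governs summaries of samples taken on Days 8 and 15 and a cell-mediated analysis that uses no Day 29 sample at all. A participant with sound predose, Day 8 and Day 15 results who misses Day 29 drops out of all of them, and the antibody results then survive only in listings.

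The same condition sits awkwardly with an interim built on data to about Day 15. Protocol 7.7 speaks of all participants in Cohorts 1 to 3, yet the only set available for the immunogenicity summaries has an entry test that falls due two weeks later. Two programmers working from the SAP could produce different interim populations. Protocol 5.6 allows unblinded safety and immunogenicity summaries to go to the Safety Review Team, and protocol 7.8 allows dose groups to be dropped partly on immunogenicity data from other groups. The composition of the interim summaries is therefore worth settling.

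**Working it through.** **1. The plan's own precision figure.** Inputs from SAP 4.1 and protocol 7.2: 30 per dose group, 10% unevaluable, SD 0.45 on the log10 scale, two-sided 95% CI.

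- Evaluable n = 30 × (1 − 0.10) = 27.
- Ratio of upper CI limit to GMI = 10^(t(0.975, n−1) × 0.45 / √n).
- n = 27: 1.507, which matches the stated 1.5.
- n = 30, with nobody lost: 1.472.

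The planned allowance of 3 in 30 thus moves the ratio only from 1.47 to 1.51. The documents give no expected Day 29 missingness, so a loss beyond that allowance cannot be computed.

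**2. What the rule removes at the final analysis.** Take a participant who is eligible, dosed per protocol, with valid predose, Day 8 and Day 15 titers and PBMC samples from Days 1 and 15, but no Day 29 titer.

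| Output | Data it needs | Participant has them? | In PP Set? |
|---|---|---|---|
| Day 8 GMT, GMI | predose, Day 8 | yes | no |
| Day 15 GMT, GMI | predose, Day 15 | yes | no |
| Day 15 seroresponse (supportive) | predose, Day 15 | yes | no |
| PBMC analysis | Day 1, Day 15 | yes | no |
| Day 29 GMT, GMI, seroresponse | predose, Day 29 | no | no |

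Only the last row needs the Day 29 condition. In the other four it removes usable data. This does not depend on any interim cut.

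**3. What the rule removes at the first interim.** Let v be the calendar day of vaccination and C the calendar day of the data cut. The Day 15 visit falls nominally at v + 14 and the Day 29 visit at v + 28.

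- A participant has Day 15 but not Day 29 data when v + 14 ≤ C < v + 28.
- If C is the last Day 15 visit in Cohorts 1 to 3, those affected were vaccinated in about the last 14 days of accrual to those cohorts.
- If C is on or after the last Day 29 visit, nobody is affected on timing grounds.
- With windows of ±3 days at both visits, the individual gap runs from (29 − 3) − (15 + 3) = 8 days to (29 + 3) − (15 − 3) = 20 days.

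The documents give neither C nor an accrual rate, so the count cannot be derived. The interim is one analysis over four dose groups (2, 4, 8 and 12 µg) whose enrollment opens in steps after safety review. A timing loss would therefore fall mainly on the last-vaccinated participants and need not recur in each group.

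**4. Whether the visible text already resolves it.** SAP Section 1 says the SAP covers the final analysis and both interims and points to Section 12. Section 12 is present and contains no interim set. SAP 8.3 and Appendix 15.2 are not in the available text, so a rule specific to PBMC outputs could exist there. SAP 4.3.2 itself, however, assigns the PBMC subset to PP.

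**The case against.** The best case for the plan has four parts.

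- **The interim is better specified than it may seem.** Cohorts, per-participant window and minimum content are stated. Because Section 12 sets a minimum and not a maximum, the cut may come late enough for Day 29 titers to be in hand. This stands: a timing loss is possible but not shown. What is missing is the analysis set and the calendar cut, and the cut alone is only a missing detail.
- **A fixed completer set has merit.** It keeps the same people at every visit and matches the Day 29 seroresponse endpoint. This stands as a reason to keep it as a sensitivity analysis. It does not justify making it the only set for Day 15 and PBMC outputs.
- **The consequences are small.** The endpoints are descriptive, the primary safety endpoints and the Day 8 safety reviews do not use PP, the second interim is cancelled, and the Safety Review Team's interim review follows a charter that is not available. Protocol 7.8 sets no numerical immunogenicity rule. All of this stands and limits the weight of the point.
- **The planned 10% unevaluable rate may already absorb the loss.** Nothing in the documents shows otherwise.

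A reader might go further and infer that the interim PP Set would be empty, or that every dose group would lose a sizeable share of its participants. The documents support neither. The first needs data truncated at Day 15 for the membership test itself. The second needs an accrual pattern and a cut date that are not given, and it ignores that the interim is a single analysis over groups opened in sequence.

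**Conclusion.** The point holds as a modest one. As written, the PP rule discards valid Day 8 and Day 15 titers, the supportive Day 15 seroresponse and PBMC results for anyone without a Day 29 titer. At the first interim it also discards anyone who has not reached Day 29 at the cut. The first part follows directly from the membership wording; the second depends on an unstated calendar cut and may be nil.

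No size can be given. The conclusion assumes that PP is applied literally and that the unavailable SAP sections contain no exception. It touches descriptive secondary and PBMC outputs and one remaining interim, and leaves the safety conclusions alone. It is worth correcting because a visit-specific rule uses more of the data already collected at almost no cost. The SAP is already part of the way there: 4.3.2 excludes individual blood results that are off schedule or follow an interfering condition.

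**What to change.** In SAP 4.3.2:

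- Require the Day 29 titer only for Day 29 endpoints.
- For every other visit, require eligibility, dosing per protocol, a predose value and a valid result at the visit analysed, with no excluding event or COVID-19 vaccination before that sample.
- Use the Day 15 version for the first interim, the Day 15 seroresponse and PBMC, and say so in Section 12. Stating the calendar cut there as well would be helpful.
- Keep the Day 29 PP Set for demography, disposition counts and exclusion listings, so that those tables need only one definition, and as a sensitivity analysis on the same people across visits.

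Cost: one flag per visit and no new data. The number analysed will differ by visit, but SAP 5.1 and 8.2.1 already plan per-visit counts, so no new table is needed. Protocol 7.3 needs matching wording, which under protocol 11.2.1 means an amendment submitted to the ethics committee. The alternative is to record the change in SAP Section 13, which now reports no changes to the planned analysis.
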